6.2 Dose modifications

6.2.1 Dose modification and dose delay

For patients who do not tolerate the protocol-specified dosing schedule, dose interruptions and/or reductions are either recommended or mandated in order to allow patients to continue the study treatment.

These dose modifications are summarized in [Table 6-2](#). Deviations to mandatory dose interruptions and/or reductions are not allowed. Permanent treatment discontinuation is mandatory for specific events indicated as such in [Table 6-2](#) or listed in [Section 6.2.1.1](#).

These dose changes must be recorded on the Dosage Administration Record CRF.

Each patient is only allowed 2 dose reductions. In addition, a patient must discontinue treatment with pazopanib if, after treatment is resumed at a lower dose, the toxicity recurs with the same or worse severity.

If a patient requires a dose interruption of >21 days from the intended day of the next scheduled dose, then the patient must be discontinued from the study treatment. Patients who discontinue study treatment for a study related adverse event or an abnormal laboratory value must be followed as described in [Section 8.1](#).

Table 6-2 Criteria for dose reduction / interruption and re-initiation of pazopanib treatment for adverse drug reactions

Investigations (Hematologic)	
Neutropenia (ANC)	
Grade 1 (ANC < LLN - 1500/mm ³)	Recommendation: maintain dose level, monitor as clinically indicated
Grade 2 (ANC < 1500 - 1000/mm ³)	Recommendation: maintain dose level, monitor as clinically indicated
Grade 3 (ANC < 1000 - 500/mm ³)	Recommendation: Step 1: Omit dose until resolved to ≤ Grade 2 Step 2: Restart pazopanib at a dose-reduced by 200 mg and monitor as clinically indicated. If no recovery to ≤ Grade 2 or recurrent Grade 3 neutropenia, discontinue pazopanib and follow-up per protocol
Grade 4 (ANC < 500/mm ³)	Mandatory: Step 1: Omit dose until resolved to ≤ Grade 2 Step 2: Restart pazopanib at a dose-reduced by 200 mg and monitor as clinically indicated. If no recovery to ≤ Grade 2 or recurrent Grade 4 neutropenia, discontinue pazopanib and follow-up per protocol
Febrile neutropenia (ANC < 1000/mm ³ , fever ≥ 38.5°C)	Mandatory: Omit dose until resolved, then restart pazopanib at a dose reduced by 200 mg
Thrombocytopenia	
Grade 1 (PLT < LLN - 75,000/mm ³)	Recommendation: maintain dose level, monitor as clinically indicated
Grade 2 (PLT < 75,000 - 50,000/mm ³)	Recommendation: maintain dose level, monitor as clinically indicated

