(B) ALT >3.0xULN to ≤5.0xULN without bilirubin elevation (defined as total bilirubin ^b ≤2.0xULN, or direct bilirubin ≤35%) and without hypersensitivity symptoms (e.g., fever, rash)	
Mandatory:
 
 1. Interrupt pazopanib. 2. Monitor subject closely for clinical signs and symptoms for liver failure. Perform full liver panel^a at least weekly until ALT is reduced to ≤ Grade 1 (3.0xULN). 
 • Subject should permanently discontinue pazopanib if ALT does not recover to ≤3.0xULN within 6 weeks 1. If ALT recovers to ≤3.0xULN within 6 weeks, subject is eligible to be re-challenged at 400 mg daily. 
 • It is desirable for the ALT level to have recovered to ≤ULN or plateaued before re-challenge to avoid discontinuation due to recurrence of ALT >3.0xULN. Discuss with study physician as needed. 2. Following re-challenge, monitor subject closely for clinical signs and symptoms. Perform full liver panel weekly for 4 weeks and, if stable, every other week for 4 weeks. 
Recurrence Stopping Criteria:
 
If ALT elevation recurs to >3.0xULN, permanently discontinue pazopanib and monitor subject closely for clinical signs and symptoms; perform full liver panel LFTs weekly or more frequently if clinically indicated until ALT is reduced to ≤ULN or stabilized.
 
If recurrent ALT elevation meets the criteria for Scenario D or Scenario E, report the event to Novartis as an SAE within 24 hours of learning of its occurrence and follow the instruction under Scenario (D) or Scenario (E) of this table as indicated below accordingly

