
(C) ALT >5.0xULN to ≤8.0xULN without bilirubin elevation (defined as total bilirubin^b ≤2.0xULN, or direct bilirubin ≤35% and without hypersensitivity symptoms (e.g., fever, rash)
	
Mandatory:
 
1. Interrupt pazopanib.2. Monitor subject closely for clinical signs and symptoms of liver failure. Perform full liver panel weekly or more frequently if clinically indicated until ALT is reduced to ≤3.0xULN. Liver imaging is optional and dependent upon clinical scenario.
• Subject should permanently discontinue pazopanib if ALT does not recover to ≤3.0xULN within 2 weeks3. If ALT recovers to ≤3.0xULN within 2 weeks, subject is eligible to be re-challenged at 400 mg daily
• It is desirable for the ALT level to have recovered to ≤ULN or plateaued before re-challenge to avoid discontinuation due to recurrence of ALT >3.0xULN. Discuss with study physician as needed.4. Following re-challenge, monitor subject closely for clinical signs and symptoms; perform full liver panel weekly for 4 weeks and, if stable, every other week for 4 weeks. 
Recurrence Stopping Criteria: If ALT elevation recurs to >3.0xULN, permanently discontinue pazopanib and monitor subject closely for clinical signs and symptoms; perform full liver panel weekly or more frequently if clinically indicated until ALT is reduced to ≤ULN or stabilized. If recurrent ALT elevation meets the criteria for Scenario D or Scenario E, report the event to Novartis as an SAE within 24 hours of learning of its occurrence and follow the instruction under Scenario (D) or Scenario (E) of this table as indicated below accordingly.

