
(D) ALT >8.0xULN without bilirubin elevation (defined as total bilirubin^b ≤2.0xULN, or direct bilirubin ≤35%) and without hypersensitivity symptoms (e.g., fever, rash)
	
Mandatory:
 
1. Permanently discontinue pazopanib.2. Report the event to Novartis as an SAE within 24 hours of learning of its occurrence and complete the eCRF liver event forms.3. Make every reasonable attempt to have subjects return to the clinic within 24 to 72 hours for repeat liver chemistries. Monitor subject closely for clinical signs and symptoms; perform full liver panel weekly or more frequently if clinically indicated until ALT is recovered to ≤ULN or stabilized.4. Liver imaging is optional and dependent upon clinical scenario. Perform liver imaging if the subject exhibits a possible biliary event (e.g., abdominal pain lasting for hours, fever, jaundice, palpable right upper quadrant mass).

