7.1.3 Discontinuation of study treatment

Patients may voluntarily discontinue from the study treatment for any reason at any time.

If a patient decides to discontinue from the study treatment, the investigator should make a reasonable effort (e.g., telephone, e-mail, letter) to understand the primary reason for this decision and record this information in the patient's chart and on the appropriate eCRF pages. They may be considered withdrawn if they state an intention to withdraw, fail to return for visits, or become lost to follow-up for any other reason.

The investigator may discontinue study treatment for a given patient if he/she believes that continuation would be detrimental to the patient's well-being.

In addition to mandatory dose interruptions and/or reductions of study treatment listed in [Table 6-3](#), study treatment must also be discontinued under the following circumstances:

- Adverse event or lab abnormality as indicated in [Section 6.2](#), or a dose interruption of more than 21 days
- Progressive disease
- Pregnancy
- Death
- Subject/guardian decision
- Lost to follow-up

Study treatment may also be discontinued if any of the following occur:

- Protocol deviation
- Study terminated by sponsor

- Technical problems
- Physician decision

Patients who discontinue study treatment should NOT be considered withdrawn from the study. They should return for the assessments indicated in [Table 7-1](#). If they fail to return for these assessments for unknown reasons, every effort (e.g., telephone, email, letter) should be made to contact them as specified in [Section 7.1.6](#).

Patients who discontinue study treatment should undergo an End of Study treatment visit followed by a 30 day safety follow-up. The “End of Treatment Phase Disposition” eCRF page must be completed, giving the date and primary reason for discontinuation.

The investigator must also contact the IRT to register the patient’s discontinuation from study treatment.

For patients who discontinue treatment for reasons other than documented disease progression, death, lost to follow-up, or withdrawal of consent before LPFV + 1 year, tumor assessments must continue to be performed every 8 weeks until documented disease progression, death, lost to follow-up, withdrawal of consent or until one year from LPFV.

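### The recurrence rule in Protocol 6.2.1 contradicts the mandatory proteinuria row of Table 6-2, and two liver re-challenge permissions in that table are overridden by stops elsewhere without the table saying so

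*Protocol*

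**What the plan says.** **General rules.** Protocol 6.2.1 allows two dose reductions, forbids departures from the mandatory steps in Table 6-2, and requires discontinuation if a toxicity comes back at the same or worse severity after treatment has resumed at a lower dose. Its limit on interruptions reads "requires a dose interruption of >21 days from the intended day of the next scheduled dose, then the patient must be discontinued". Section 7.1.3 repeats this: "study treatment must also be discontinued under the following circumstances", and its list includes an adverse event or laboratory stop "or a dose interruption of more than 21 days". Section 6.2.1 makes permanent discontinuation mandatory for events so marked in Table 6-2 or listed in 6.2.1.1. For a patient with normal baseline values, 6.2.1.1 calls for immediate discontinuation when AST or ALT exceeds 3xULN together with total bilirubin above 2xULN.

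**Table 6-2, proteinuria (mandatory).** At UPC ≥3 or 24-hour protein ≥3 g: interrupt, monitor weekly, and restart 200 mg lower. On recurrence, do the same again. Stop for good only if the problem persists at 400 mg.

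**Table 6-2, other non-liver Grade 3 events (recommended).** Interrupt, restart 200 mg lower, and on recurrence of Grade 3 interrupt or reduce further.

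**Table 6-2, liver.** Scenario B (ALT >3 to 5xULN): "If ALT recovers to ≤3.0xULN within 6 weeks, subject is eligible to be re-challenged at 400 mg daily". Scenario C (ALT >5 to 8xULN): "If ALT recovers to ≤3.0xULN within 2 weeks, subject is eligible to be re-challenged at 400 mg daily". Both scenarios are for patients without bilirubin elevation, which they define as total bilirubin ≤2xULN "or direct bilirubin ≤35%) and without hypersensitivity symptoms" in B and "or direct bilirubin ≤35% and without hypersensitivity symptoms" in C. Scenarios D and E both say "Permanently discontinue pazopanib".

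**The concern.** A site managing toxicity will normally work from the relevant row of Table 6-2. In the proteinuria case, following the row breaks 6.2.1 and following 6.2.1 breaks the row, and both are mandatory. In the liver cases, a site that reads only the row could restart pazopanib in a patient whom 6.2.1, 7.1.3 or 6.2.1.1 says must stop.

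Hepatic toxicity is an adverse event of special interest (Protocol 8.1.3), and the bilirubin pattern is foreseeable. Footnote c of the liver rows says that pazopanib can raise indirect bilirubin without liver injury, and footnote b requires fractionation once total bilirubin exceeds 2xULN, so a direct fraction will usually be known.

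There is also a reporting consequence. Protocol 12 permits no authorized deviations, and SAP 2.3 tabulates deviations by category. The same action could be classed as compliant under one text and as a deviation under another. Discontinuation and exposure summaries would also depend on which text a site followed.

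**Working it through.** The plan gives no figure to reproduce here. The check sets the rules side by side, with simple counts.

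**1. Proteinuria.** Inputs: dose steps 800, 600 and 400 mg (Table 6-3); at most two reductions (6.2.1); the recurrence rule (6.2.1); the proteinuria row (Table 6-2). Assume that the recurrence is of the same or worse severity. Restarts allowed:

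| Dose at first episode | Table 6-2 | 6.2.1 | Difference |
|---|---|---|---|
| 800 mg | 2 (at 600, then 400) | 1 (at 600) | 2 − 1 = 1 |
| 600 mg | 1 (at 400) | 1 (at 400) | 0 |
| 400 mg | 0 | 0 | 0 |

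The conflict therefore arises only when the first episode is on 800 mg and the recurrence is on 600 mg. Example: UPC 3.5 on 800 mg, restart at 600 mg, UPC 3.5 again. Section 6.2.1 says discontinue. The row says interrupt and restart at 400 mg. No action satisfies both.

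**2. Other non-liver Grade 3 events.** After the first episode the patient restarts 200 mg lower. A second Grade 3 episode on that dose is a recurrence at the same severity, so 6.2.1 requires a stop where the row allows interruption or further reduction. The row is a recommendation and is worded permissively, so stopping breaks nothing mandatory.

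**3. Scenario B against the 21-day limit.** Scenario B window: 6 × 7 = 42 days. General limit: 21 days. Excess: 42 − 21 = 21 days, so the second half of the window cannot be used if 6.2.1 and 7.1.3 are followed. Scenario C's window is 2 × 7 = 14 days, inside the limit. The 21-day rule counts the length of the interruption, not the day on which ALT recovers. Scenario B also prefers to wait for ALT ≤ULN or a plateau, so a patient who recovers before day 21 may restart after it. The affected group is best described as any re-challenge after an interruption of more than 21 days.

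**4. Scenarios B and C against 6.2.1.1.** Take normal baseline ALT, AST and bilirubin, no hypersensitivity symptoms, and total bilirubin 2.5xULN:

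| ALT | Direct fraction | Table 6-2 | 6.2.1.1 |
|---|---|---|---|
| 4xULN | 30% | B: interrupt, may re-challenge | Discontinue |
| 6xULN | 30% | C: interrupt, may re-challenge | Discontinue |
| >8xULN | 30% | D: permanent stop | Discontinue |
| >3xULN | >35% or not available | E: permanent stop | Discontinue |

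The mismatch is confined to the first two rows: ALT >3 to 8xULN, total bilirubin >2xULN and a measured direct fraction ≤35%. Hypersensitivity symptoms would move the patient to Scenario E, also a stop. A rise in AST alone falls in neither B nor C. For patients with abnormal baseline values, 6.2.1.1 adds conditions relative to baseline, so the overlap is narrower.

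**The case against.** The strongest reply is that the liver cases are already settled. Re-challenge is only something the patient is eligible for. The 21-day stop is unqualified, 7.1.3 presents its stops as additional, and 6.2.1 names 6.2.1.1 as a ground for permanent discontinuation in its own right. A site that stops complies with every text. This stands. A reader might infer three outright contradictions; the documents support one, plus two permissions that have no effect when the whole section is read. What remains is that Table 6-2 does not say so.

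For proteinuria, one can argue that a specific mandatory row governs a general sentence, and that stepping down twice fits the two-reduction allowance. That is plausible, but neither document states it. The same convention applied to Scenario B would favor re-challenge, whereas a strictest-rule convention would favor stopping.

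A reader might also infer that a milder recurrence with UPC still ≥3 escapes 6.2.1. The documents do not establish this: Protocol 8.1.1 grades severity by CTCAE, and nothing maps UPC values to grades. The clear conflict is a recurrence that is the same or worse.

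Other mitigations are fair. Scenarios B and C tell sites to discuss re-challenge with the study physician as needed. Protocol 12.1 leaves room for immediate safety action. Deviation categories sit in a separate specification document, which may already settle classification.

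**Conclusion.** The point holds in limited form and should be fixed. There is one true contradiction between mandatory instructions: a same-or-worse proteinuria recurrence on 600 mg after a first episode on 800 mg, where the texts differ by one restart. The recommended row for recurrent Grade 3 events meets the same rule. Two liver permissions are overridden by mandatory stops elsewhere without a cross-reference.

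The reach is small. The documents give no frequencies for any of these patterns, the 21 excess days are a span of time and not a share of patients, and 8 patients remained on treatment at Amendment 2.

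A reader might infer damage to the primary result; the documents do not support that. Patients who stop without progression continue tumor assessments until one year after the last patient's first visit (Protocol 7.1.3), SAP 2.5.3 does not censor PFS at treatment discontinuation, and no hypothesis is tested. Any effect on PFS is indirect, through how long patients stay on drug. The substance is patient safety and consistent reporting of discontinuation, exposure and deviations.

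The conclusion assumes that no separate instruction to sites, outside these documents, already sets an order of precedence.

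**What to change.** - **Recurrence rule (6.2.1).** Add *unless Table 6-2 specifies otherwise*. This resolves both the proteinuria row and the recurrent Grade 3 row. Editing the proteinuria row alone would leave the second untouched.
- **21 days against 6 weeks.** Either write an explicit Scenario B exception into 6.2.1 and 7.1.3, or shorten Scenario B to 21 days.
- **Scenarios B and C.** State that patients who meet 6.2.1.1 must be permanently discontinued whatever the direct fraction. If the sponsor judges that an indirect bilirubin rise should not force a stop, add a direct-fraction condition to 6.2.1.1 instead. The SAP 2.8.3 liver categories carry no direct-fraction condition, but they are descriptive tabulations and do not decide this medical choice.
- **Until amended.** Tell sites that the stricter stop applies in the liver cases, and which rule applies to proteinuria.

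The cost is a few sentences in an amendment or a site clarification letter. No new procedures or analyses are needed.

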Study VEG108844 is a randomized, open-label, parallel group Phase III non-inferiority study to evaluate the efficacy and safety of pazopanib compared with sunitinib in subjects with advanced RCC who had not received prior systemic therapy for advanced or metastatic RCC. Approximately 876 eligible subjects (approximately 438 per treatment arm) were planned to be enrolled over the course of the study. However, due to higher than expected withdrawal rates and discordance rates between Independent Review Committee (IRC) and investigator assessments of progression, the protocol was amended to increase the number of subjects to approximately 1100 total by including all subjects enrolled in VEG108844 and VEG113078 (a substudy of VEG108844). VEG113078 was conducted in China, Korea, and Taiwan; enrolled the same subject population as VEG108844; and is almost identical in study design and conduct to allow integration of efficacy and safety data.

A total of 1102 subjects were included in the safety population (pazopanib 554 subjects; sunitinib 548 subjects). At the time of the OS analysis (data cut-off 30 September 2013) the median time on treatment was 8.1 months for pazopanib and 7.6 months for sunitinib. The overall frequency of AEs reported during the study was similar for each treatment group; 552

subjects (>99%) had AEs in the pazopanib arm and 544 subjects (>99%) had AEs in the sunitinib arm. However, differential safety profiles were observed between the treatment arms, with a statistically significant difference in frequencies (unadjusted for multiplicity) for several AEs. The most common AEs (>35% in either treatment arm) were diarrhea (63% in pazopanib arm, 57% in sunitinib arm), fatigue (55% in pazopanib arm, 63% in sunitinib arm), hypertension (47% in pazopanib arm, 41% in sunitinib arm), nausea (45% in pazopanib arm, 46% in sunitinib arm), decreased appetite (38% in pazopanib arm, 37% in sunitinib arm), dysgeusia (26% in pazopanib arm, 36% in sunitinib arm), and palmar-plantar erythrodysesthesia (PPE) syndrome (or hand-foot syndrome [HFS]) (30% in pazopanib arm, 50% in sunitinib arm).

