(B) Asymptomatic SBP ≥160 mmHg, or DBP ≥100 mmHg	Highly recommended: Step 1. Dose reduce by 200 mg or interrupt pazopanib as per clinical judgment Step 2. Adjust current or initiate new antihypertensive medication(s) ^e to achieve and maintain a BP level of < 140/90 mmHg. If BP can be controlled to < 140/90mmHg within 3 weeks and pazopanib has been interrupted, it can be resumed with dose reduced by 200 mg from the pre-event dose. If BP cannot be adequately controlled with these measures, consider referring the subject to a specialist for further evaluation and management.
(C) Symptomatic hypertension or recurring SBP≥160 mmHg, or DBP≥100 mmHg, despite modification of antihypertensive medication(s)	Highly recommended: Step 1. Interrupt pazopanib Step 2. Strongly recommend referring the subject to a specialist for further evaluation and management Once BP is controlled to <140/90mmHg via adjustment of current or initiating new antihypertensive medication(s) ^e , pazopanib can be resumed with dose reduced by 200 mg. BP should be monitored as clinically indicated

(D) Refractory hypertension unresponsive to above interventions including malignant hypertension, hypertensive crisis, transient or permanent neurological deficit related to uncontrolled hypertension.		Mandatory: Permanently discontinue pazopanib and continue follow-up per protocol.		
d. Persistent SBP and/or DBP is defined as SBP of ≥ 140 or DBP ≥ 90 for at least 24 hours per NCI-CTCAE v4.03 Recommendation of antihypertensive agents for treatment-emergent BP elevations: ACE inhibitors, angiotensin receptor blocking agents, beta blockers, calcium channel blockers and diuretics have all shown to reduce blood pressure in subjects treated with pazopanib				
Gastrointestinal				
Pancreatitis				
Grade 2	Recommendation: Maintain dose level			
Grade ≥ 3	Mandatory: Omit dose and discontinue patient from pazopanib			
Diarrhea**				
Grade 1	Recommendation: Maintain dose level but, initiate anti-diarrhea treatment			
Grade 2	Recommendation: Omit dose until resolved to \leq grade 1, then maintain dose level. If diarrhea returns as \geq grade 2, then omit dose until resolved to \leq grade 1, then reduce dose by 200 mg. Omit dose until resolved to \leq grade 1, then reduce dose by 200 mg			
Grade 3	Recommendation: Omit dose and discontinue patient from pazopanib			
Grade 4	Mandatory: Omit dose Mandatory: Discontinue patient from pazopanib			
Skin and subcutaneous tissue disorders				
Rash/photosensitivity				

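### Table 6-2 gives two conflicting recommendations for a first recurrence of diarrhea at Grade 3 after a Grade 2 episode: reduce and continue, or stop pazopanib

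*Protocol*

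**What the plan says.** The diarrhea block of Table 6-2 is organised by grade.

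- **Grade 2 row (a recommendation).** After a first episode the drug is held until recovery and restarted at the same level. The row then adds a recurrence clause: "If diarrhea returns as \geq grade 2, then omit dose until resolved to" grade 1 or lower, followed by a 200 mg reduction. (The symbol in the quote is the at-least sign.)
- **Grade 3 row.** "Recommendation: Omit dose and discontinue patient from pazopanib".
- **Grade 4 row.** The hold is mandatory, and so is the stop: "Mandatory: Discontinue patient from pazopanib".

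The text of Section 6.2.1 distinguishes recommended from mandated modifications. It states that "Deviations to mandatory dose interruptions and/or reductions are not allowed", and it makes permanent discontinuation mandatory wherever the table marks it so. It also requires discontinuation if a toxicity comes back at the same or greater severity once treatment has been resumed at a lower dose. A footnote to Table 6-2 ties dose modifications to the worst preceding toxicity.

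**The concern.** The recurrence clause in the Grade 2 row has a lower limit but no upper one, so read literally it also governs recurrences at Grades 3 and 4. The rows for those grades call for stopping and make no exception for a recurrence. Where two rows apply to one event and give opposite instructions, two sites can each follow the protocol and act differently.

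The row decides whether a patient stays on drug, which is a safety matter. It also feeds a planned result. Protocol Section 10.5.3.6 assesses tolerability partly by the incidence of events leading to study treatment discontinuation, and SAP Section 2.8.1 tabulates adverse events by that outcome. If the stop-or-continue choice depends on which row a site reads, part of that count reflects the reading rather than the drug.

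**Working it through.** No statistical figure is involved, so the check is a reading of the rows against each other and against the general rules.

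**Step 1. The case.** A patient has Grade 2 diarrhea, recovers, and resumes at the same dose as the Grade 2 row directs. Diarrhea then returns for the first time.

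**Step 2. Which rows apply, by grade at return.**

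| Grade at return | Grade 2 row, recurrence clause | Row for that grade | Result |
|---|---|---|---|
| 2 | Hold, then 200 mg lower (recommendation) | The same row | One action |
| 3 | Hold, then 200 mg lower (recommendation) | Hold and discontinue (recommendation) | Two opposite actions of equal standing |
| 4 | Hold, then 200 mg lower (recommendation) | Hold and discontinue (mandatory) | Wording overlaps; the mandatory stop prevails |

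**Step 3. Does the recurrence rule in Section 6.2.1 settle Grade 3?** No. It starts only after treatment has been resumed at a lower dose, and here it was resumed at the same dose: "grade 1, then maintain dose level. If diarrhea returns as" comes before any reduction. The rule does cover a later return at the same or worse severity, once a reduction has been made.

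**Step 4. Does the footnote settle it?** Not expressly. It says that the worst preceding toxicity drives the modification. It does not say which row governs when a lower-grade row itself prescribes for higher-grade recurrences.

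**Step 5. Does the table handle recurrence more clearly elsewhere?** Yes. The Grade 3 neutropenia row names the recurrent grade it covers. The hemorrhage block puts Grade 3 or 4 events and recurrences at grade 2 or above into one row with one action. The diarrhea block does neither.

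**Step 6. How secure is the text?** The Grade 2 cell ends with an unlabelled repeat of the hold-and-reduce instruction, visible where "grade 1, then reduce dose by 200 mg. Omit dose until resolved to" runs two sentences together. It stands directly before the Grade 3 row and may have moved when the PDF table was read. The recurrence clause comes before it, so the reach of that clause does not depend on it. The content of the Grade 3 row might. If the stray sentence belongs there alongside the discontinuation instruction, the Grade 3 row would itself contain both reduce and stop.

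**Step 7. Size.** The affected path is Grade 2, recovery, resumption at the same dose, then first return at Grade 3. The protocol's background section reports diarrhea in 45%, 52%, 63% and 66% of pazopanib patients across four renal cell carcinoma studies. These are any-grade figures, with no split by grade or recurrence, so they give no count for this path.

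**The case against.** The best defence is that the table is arranged by event grade, so a site facing a Grade 3 event would naturally go to the Grade 3 row, and the footnote leans the same way. Both competing actions are also only recommendations. Section 6.2.1 bars deviation only from mandatory modifications, and Section 7.1.3 lets the investigator stop treatment on clinical judgment, so some variation between sites is built into the design.

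Part of this stands. A site may well reach an answer by inference, and the protocol does tolerate discretion here. But discretion to depart from a recommendation is different from having two opposite recommendations, and nothing in the documents states the inference.

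Several stronger readings are tempting and not supported:

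- **That any recurrence at grade 2 or worse has two actions.** At Grade 2 only one row applies.
- **That the plan leaves Grade 4 open.** The mandatory status settles it.
- **That the Grade 2 cell contradicts itself.** That rests on the unlabelled sentence, which may be displaced.
- **That tolerability is measured by dose reductions.** Section 10.5.3.6 uses drug-related events by grade and events leading to discontinuation. Reductions are summarised with treatment data (Protocol Section 10.3, SAP Section 2.4.1).
- **That stopping drug ends observation of progression.** Patients who stop without progression before one year after the last patient's first visit keep having tumor assessments every 8 weeks, up to that one-year point (Protocol Sections 7.1.3 and 7.1.5.2).
- **That 45 to 66 of 100 patients are affected.** Those are any-grade rates, and the protocol notes that most of the common events in one of these studies, VEG105192, were Grade 1 or 2.

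**Conclusion.** The point holds in a narrow form. For a first recurrence of diarrhea at Grade 3, after a Grade 2 episode resumed at the same dose, Table 6-2 gives two incompatible recommendations of equal standing, and no other rule in the documents says which governs. The consequence is a possible stop-or-continue difference between sites for the same event, with an effect on patient safety and on the count of events leading to discontinuation. The documents do not allow the number of patients to be estimated, and no effect on the primary analysis is claimed.

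The conclusion assumes that the Grade 3 row appears in the source table as it was read here. If the source differs in that row, the conflict could shift or disappear, so that check comes first. No view is taken on which action is right.

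**What to change.** Check the diarrhea block of the source table, in particular where the unlabelled hold-and-reduce sentence belongs. Then reconcile the rows so that each grade, first or recurrent, has one action, and state which grades the recurrence clause in the Grade 2 row covers. The sponsor's clinical team decides which action is intended; none is proposed here.

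The cost is a wording change in one table block, by amendment or clarification letter. The prospective benefit is limited, because 8 patients remained on treatment at the date of Amendment 2. For events that have already occurred, the study report could state which row sites followed when a Grade 3 recurrence led to stopping or to a reduction.
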